1.1 Introduction

Globally around 15 million infants are born premature (<37 weeks gestation) annually which accounts to more than 1 in 10 live births and it's a leading cause of neonatal mortality and morbidity(1, 2). Most common complications of preterm birth are respiratory distress syndrome, bronchopulmonary dysplasia, necrotizing enterocolitis, sepsis, periventricular leukomalacia, seizures, intraventricular hemorrhage, feeding difficulties, hypoxic ischemic encephalopathy, and visual and hearing problems(3-6). However, advances in neonatal intensive care has improved the survival of sick and vulnerable newborns, particularly infants born preterm but the rate of disability has relatively remained constant, with up to 50% of these infants later exhibiting developmental disabilities such as motor, cognitive or behavioral impairments(4, 6-11). These developmental disabilities are complex, diverse and impact multiple domains which restricts participation in home, at school and in community which ultimately affect the overall quality of life of the child and the family(12).

The effects of premature birth are not only experienced by the infants but also by the parents. The parents commonly experience helplessness, fear, loss and inadequacy(13, 14). Over the course of hospitalization parents feel increased stress, anxiety and depression(15, 16). Some parents also demonstrate symptoms of post-traumatic stress disorder(17). The emotional stress on parents of the infants born preterm can lead to disruptive interactive pattern with their infants which may have long term adverse effect on attachment pattern, affective state regulation, social interaction and overall developmental outcomes on the infant(18). Therefore, families of infants born preterm often experience immense psychological stress and financial burden due to prolonged stay and the infant requiring repeated admission in the hospital which further leads to significant cost to health system(19-21).

The preterm period is very crucial period in terms of high risk for injury to the brain as well as sensitive time frame for motor development (22). According to the dynamic system theory, motor development is believed to be a feedback process based on interaction among

different subsystems in the child, the environment and the task. Studies have established that motor and cognitive development go hand in hand such that delay in one domain can contribute to delay in another domain(23, 24). Typically developing infants uses movement to communicate and learn about the object by interacting physically with the environment allowing the development of other developmental domains besides motor, especially cognition which is usually impaired in children born preterm(25, 26). Postural control is the pre-requisite for development of motor skills which is usually impaired in infant born preterm which is later associated with motor impairments persisting throughout childhood(27, 28).

As infant's brain is highly plastic, interventions which focusses on enhancement of parent-child interaction, adaptation of environment to promote motor, social or cognitive development and parent education to promote developmental skill in the infant has been found effective (29-32). Numerous studies also focuses on interventions which involves active participation from the infants as it leads to structural and functional changes in the brain infant born preterm to promote neuroplasticity and as it is more likely to have maximum impact on the motor development of infant born preterm(33, 34). Since preterm period is considered sensitive time frame for motor development, intervention focused on motor skills might be beneficial for motor development in infants born preterm.

With the advancement of medical services the survival of preterm infants has improved but the developmental services to these vulnerable population continues to be “wait and watch” approach and they miss out on the critical period to start early intervention (35). There is growing evidence suggesting that early intervention is more effective in improving developmental outcomes in preterm infants compared to interventions which are started later in life(36-40). But most of these published studies on early interventions are laborious, time consuming and resource intensive limiting its use on a large scale particularly in some medical resource limited settings and are applicable in high income countries. Since there is a growing emphasis on evidence-based practice, physical therapy has come under criticism for not evaluating and providing evidence based interventions in infants born preterm (41) and as there is limited study on the effect of early physical therapy intervention (38), there is a need to study the effect of physical therapy intervention provided in a resource limited medical settings to improve the developmental outcome in infant born preterm.

With the launch of Every Newborn Action Plan at the sixty-seventh World Health Assembly in 2014, the focus of care has shifted from mere survival of newborns to thriving well especially among vulnerable small and sick newborns. The Nurturing Care Framework for Early Childhood Development, launched by WHO, UNICEF and the World Bank Group,

demonstrates that focusing on early childhood development is one of the wisest investments a country can make to boost economic growth. Therefore, there is a need of efficacious early intervention with clear evidence to optimize outcomes in preterm infants so that the preterm infants and families benefit in the long run.

At Jigme Dorji Wangchuck National Referral Hospital (JDWNRH), Thimphu Bhutan the prevalence of preterm birth was 6.4% (64 per 1000 live birth)(42). This study will be conducted at JDWNRH which is a tertiary care hospital with NICU facility. The participants for the study will be low risk preterm infants since these group of infants are followed up periodically to monitor for developmental outcome, the follow up starts only when the child attends 3 months of corrected age and they miss out on the critical period to start intervention. In Bhutan, due to a shortage of pediatric physical therapists (PT), this group of infants does not receive proper attention and if the parents are taught how to provide a home programme, it helps in empowering the parents and reducing the burden and stress of bringing the child for therapy at the clinic regularly. This will also help the limited number of PTs in the country to provide better care and support to the high-risk preterm infants.

Most of the early intervention programs are resource intensive and requires a multi-disciplinary team. In a setting where there is limited human resources, customized physical therapy intervention will empower parents to provide intervention to their infant within the natural environment of their home with no extra resources required. Involving parents as primary practitioners will help them to understand and respond more knowledgeably to their infant's behaviour, which can promote optimal development. Therefore, the long-term outcome of this study is to provide appropriate physical therapy intervention to infants born preterm post discharge from the neonatal unit so that it can improve the motor development and prevent the neurodevelopmental impairments. The findings from this study will help in providing appropriate physical therapy intervention which involves parent, therapist and infant interactions to enhance the motor development of infants born preterm.

1.2 Conceptual framework

[figure not shown]

Figure 1: Conceptual framework

1.3 Objectives

To investigate the effect of modified supporting play, exploration and early development (SPEEDI) on neuromotor performance in infants born preterm when the intervention is provided by the parents post discharge from Neonate Intensive Care Unit (NICU) compared to infants born preterm receiving standard care at 3 months of corrected age

1.3.1 Specific objective

1. To compare the difference in motor performance between infants born preterm receiving modified supporting play, exploration and early development intervention (SPEEDI) and standard care at baseline, 1 month, 2 months and 3 months of corrected age.
2. To compare the difference in neurodevelopment between infants born preterm receiving modified supporting play, exploration and early development (SPEEDI) and standard care at baseline, 1 month, 2 months and 3 months of corrected age
3. To compare the compliance of parents with infants born preterm receiving modified supporting play, exploration and early development intervention (SPEEDI) and standard care.

1.4 Study design

The proposed study will be single-center, prospective, double-blinded randomized controlled trial (RCT) to study the effect of physical therapy intervention on motor performance of infant born preterm.

1.4.1 Study setting

All data collection will be performed at Pediatric Physiotherapy Unit, Jigme Dorji Wangchuck National Referral Hospital (JDWNRH), Thimphu Bhutan.

1.4.2 Participants

During the study period infants born preterm (<37 weeks) at Neonatal Intensive Care Unit (NICU) of Jigme Dorji Wangchuck National Referral Hospital (JDWNRH), Thimphu Bhutan meeting the following inclusion and exclusion criteria shall be recruited for the study.

1.4.3 Inclusion criteria

- Infants who are born <37 weeks' gestation
- Medically stable and off ventilator on discharge from NICU
- Parents who consent to come for follow up.

1.4.4 Exclusion criteria

Infants will be excluded from the study if they have

- Cortical blindness or retinopathy of prematurity causing blindness
- Musculoskeletal/congenital abnormalities
- Brain injuries including intraventricular hemorrhage (grade 3 and above), hypoxic ischemic encephalopathy and hydrocephalus
- Genetic syndrome
- Infants undergone major surgery
- Family who do not consent
- Parent with physical and psychological problems
- Infants with medical devices such as NG tube and gastrostomy

1.4.5 Sample size

Sample size calculation will be based on the study by Dusing et al(43). According to the study they found a significant difference in motor performance of infants born preterm who received physical therapist delivered intervention compared to the usual care group. The effect size from the study was Cohen's d of 1.29 for TIMP z- score. Using this data, the total sample size of 22 was obtained using G power program version 3.1. However, with 20% drop out rate a total of 28 infants born preterm would be required with 14 in each group.

[figure not shown]

Figure 2: G power

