1.4.6 Variables

Independent variable

1. Groups: Intervention group and standard care group
2. Time: At baseline, 1, 2 and 3 months of corrected age

Dependent variable

1. Motor performance
2. Neurodevelopment
3. Compliance

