The Phase I of the original version of SPEEDI consist of parent therapist collaborative sessions to understand infant cues, readiness for interaction, developmental support and stressors, ideas to promote interaction and development and watching the videos which is provided during the stay in NICU. However, this phase I intervention will be provided post discharge from the NICU at 40 weeks. The main objective of making parents watch these videos would be to help parents interact with their infant and perform the activities at home since most of the parents would be anxious and not know how to interact with their infant. The Phase II from the original version consisted of home visit to provide the intervention post discharge from NICU. It consists of therapist guiding the parents to perform play-based activities at home with their infants and these activities can be performed as a part of daily activities with their infants especially during feeding, bathing and changing diapers. There are 5 main activities which the parents must perform with their infant at home. The activities are broken down into three stages that become progressively challenging over time. For this study purpose the phase II intervention will be provided at the hospital where the parent will need to bring their infant to the hospital and the 5 main activities will be broken down into two stages. During the monthly visit the principal researcher will assess and decide the infant's ability to progress the activity from stage 1(easy) to Stage 2(hard). If the infant is found to be not ready to progress to the next stage, they will continue with the same activity. The primary caretaker will be given activity booklet which will contain pictures, simple text and log to record daily

activities. To perform the play- based activities the primary caretaker will be asked to use toy within their natural home environment since the intervention does not require any specific or sophisticated toys.

Intervention	40 weeks	1 month	2 months
Activities	
 • Watching videos to understand cue-based interaction with the infant. • Introduce the activities that the parent can complete at home to promote midline and tracking of toys and faces 	
 • Watching people and toy • Tummy time • Holding head up • Kicking • Toy play 	
 • Watching people and toy • Tummy time • Holding head up • Kicking • Toy play

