1.4.10 Statistical Analysis

Statistical analysis will be performed using Statistical Package for Social Sciences (IBM SPSS statistics for windows, version 28). Shapiro Wilk test will be used to test for normality of data. Descriptive statistics will be used to analyze patient's demographic data. To investigate the effect of physical therapist intervention on motor performance two-way mixed ANOVA will be performed. To investigate the effect of physical therapy intervention on neurodevelopment two-way mixed ANOVA will be performed. The level of significance will be set at a p-value < 0.05.

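### The 22 evaluable infants in 1.4.5 do not carry their implied power over to the mixed ANOVA in 1.4.10, which is the only motor analysis planned and names no deciding term

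*Combined protocol and SAP*

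**What the plan says.** Section 1.4.5 rests on one published effect: "The effect size from the study was Cohen's d of 1.29 for TIMP z- score". It continues: "Using this data, the total sample size of 22 was obtained using G power program version 3.1". Dropout is then added: "However, with 20% drop out rate a total of 28 infants born preterm would be required with 14 in each group". The text gives no test family, power, sidedness, between-visit correlation, or age at which the 1.29 was observed. These may be in the image captioned "Figure 2: G power", which is not reproduced in the copy reviewed; its absence is not counted against the plan.

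Section 1.4.10 gives the motor analysis: "To investigate the effect of physical therapist intervention on motor performance two-way mixed ANOVA will be performed". The only other parameter is alpha: "The level of significance will be set at a p-value < 0.05". The time factor in 1.4.6 has four levels: "Time: At baseline, 1, 2 and 3 months of corrected age". Neither the Group term nor the Group x Time term is named as deciding, and no two-group test at a single visit is planned, although the objective in 1.3 is framed at 3 months corrected age.

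Section 1.4.8 places the first measurement at 40 weeks post-menstrual age. Section 1.4.8.4 starts the programme at that same age: "However, this phase I intervention will be provided post discharge from the NICU at 40 weeks".

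**The concern.** A sample size is informative only for the test it was computed for. A single d describes one contrast between two groups. A mixed ANOVA offers two candidate terms, and each uses the four visits differently. The Group term averages the between-group difference over all visits, including one where it should be nil. The Group x Time term asks whether the difference changes, and spreads that question over 3 degrees of freedom. Neither has the power of a single comparison at d = 1.29, except by coincidence of effect shape and correlation.

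A reader of 1.4.5 would take 22 as adequate for whichever term is reported. If the effect builds gradually, a non-significant term could be read as no effect in a trial believed to be well powered, even though the assumed 1.29 had been fully achieved at 3 months.

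**Working it through.** **Inputs from the plan.** d = 1.29, N = 22 (11 per arm), 20% dropout, 28 recruited (1.4.5); alpha 0.05 (1.4.10); four visits including baseline (1.4.6).

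**Inputs assumed, because the plan gives none.** Two-sided testing; SD 1 at each visit; d = 1.29 holding at 3 months on the analysed scale; baseline measured before the first session, so expected difference zero; between-visit correlation ρ; shape of the effect over time.

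**Step 1: reproduce 22.**

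*Two-sample t-test.* Noncentrality = d × √(n/2), df = 2n − 2.
- n = 10 per arm: 1.29 × √5 = 2.885, critical t 2.101, power 77.9%.
- n = 11 per arm: 1.29 × √5.5 = 3.025, critical t 2.086, power 82.1%.

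So 11 per arm, 22 in total, is the 80%-power answer. With 11 per arm, 80% power needs d of about 1.26. Dropout: 22 / 0.8 = 27.5, rounded up to 28. The arithmetic is consistent.

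*Repeated-measures between-factors routine.* f = d/2 = 0.645, m = 4, λ = f² × N × m / (1 + (m − 1)ρ).
- ρ = 0.5, N = 22: 0.4160 × 88 / 2.5 = 14.64, power 95.3%. N = 20 gives 93.2%, so 22 is the 95%-power answer.
- ρ = 0.7: 22 is likewise the 90%-power answer.

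This formula assumes the same 1.29 at all four visits.

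*Within-between interaction routine.* With f = 0.645 and ρ = 0.5, 8 infants already give 98%, so this is not the source of 22.

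**Step 2: power of the planned terms, 11 per arm, linear build 0, 0.43, 0.86, 1.29.**

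*Group.* Mean difference = (0 + 0.43 + 0.86 + 1.29)/4 = 0.645. Under equal correlation, the variance of an infant's four-visit mean is (1 + 3ρ)/4. Noncentrality = 0.645 × √5.5 / √((1 + 3ρ)/4). At ρ = 0.5 this is 0.645 × 2.345 / 0.791 = 1.91 against critical t 2.086.

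*Group x Time.* Sum of squared deviations of the four differences from 0.645 = 0.645² + 0.215² + 0.215² + 0.645² = 0.9245. λ = 5.5 × 0.9245 / (1 − ρ) = 5.085 / (1 − ρ), i.e. 7.26, 10.17 and 16.95 at ρ = 0.3, 0.5 and 0.7, with df 3 and 60.

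| Correlation pattern | Term | 0.3 | 0.5 | 0.7 |
|---|---|---|---|---|
| Equal | Group | 55% | 44% | 37% |
| Equal | Group x Time | 58% | 74% | 93% |
| AR(1) | Group | 64% | 52% | 42% |
| AR(1) | Group x Time (simulated) | 49% | 57% | 72% |

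The AR(1) Group x Time figures use an uncorrected F; with the Greenhouse-Geisser correction they are about 45/52/67%. Eleven of the twelve cells lie below 82%.

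**Step 3: where the shortfall disappears.**
- Linear build, equal correlation: Group x Time reaches 82% at ρ of about 0.58 and 99% at 0.8.
- Linear build, AR(1) 0.8: Group x Time about 85%.
- Full 1.29 from 1 month, ρ = 0.5: Group 78%, Group x Time 87%.
- Profile 0, 0.86, 1.29, 1.29, ρ = 0.5: Group x Time 82%. Under AR(1) 0.3, Group is 87%.
- Profile 0, 0, 0.645, 1.29, ρ = 0.5: Group x Time 83%, but Group only 28%.

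**The case against.** The strongest reply is that 22 may have come from the between-factors routine, which is the Group term of the planned ANOVA. The charge of a test missing from 1.4.10 would then fail. This stands as far as attribution goes: a reader might infer that the authors sized the trial on a t-test, but with Figure 2 unread the documents do not show that. It does not rescue the implied power. That route needs a 1.29 difference at the 40-week baseline, which randomisation rules out in expectation.

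Second, the size of the shortfall rests on an effect shape and correlations that are not in the plan, and the plan does not say at what age 1.29 was observed. This stands. A reader might conclude that every ANOVA term is underpowered; Step 3 shows otherwise.

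Third, with no deciding term named, one could claim success if either term is significant. Under the linear build that happens in roughly 79% to 96% of trials across the correlations tabulated, close to or above the t-test's 82%. But two tests at 5% carry a false-positive risk of about 1 − 0.95² = 9.75%. This reply therefore confirms that the unnamed deciding term is the heart of the problem.

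Fourth, nothing is miscalculated. That also stands: 22 and 28 both reproduce.

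**Conclusion.** The point holds as a mismatch between the sample-size statement and the planned analysis. It is neither an arithmetic error nor an argument that 28 infants are too few. On both routes that reproduce 22, the implied power (82%, or 95% at correlation 0.5) does not carry over to the ANOVA that will be run.

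Under the linear build, the Group term is well short at every correlation tabulated (37% to 64%). Group x Time ranges from 49% to 93%, depending on the size and pattern of correlation. These figures are conditional on 11 evaluable infants per arm, SD 1 at each visit, zero expected difference at baseline and d = 1.29 at 3 months. The firm part needs none of the assumed shapes: the plan does not say which test 22 serves or which ANOVA term decides.

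**What to change.** Keep 28 infants, and align the two sections.

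- **1.4.10:** name the between-group comparison of TIMP at 3 months corrected age as the deciding motor test, since that is the time point in the objective (1.3). Preferably adjust it for the baseline TIMP already collected. Keep the two-way mixed ANOVA as a supporting analysis.
- **1.4.5:** state that 22 evaluable infants (11 per group) give 82% power, two-sided 5%, for that comparison unadjusted if d = 1.29, and 80% at d of about 1.26. Add that this figure does not apply to the mixed ANOVA terms, and that a non-significant ANOVA term will not be reported as evidence of no effect.
- **Figure 2:** check that it shows this test, and replace it only if it does not.

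Both changes are needed. Rewording 1.4.5 alone would tie 22 to a comparison that 1.4.10 still lacks.

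The cost is a few sentences and possibly one figure, with no extra infants, visits or staff. The downside is that the ANOVA becomes supportive and the claim made for 22 becomes narrower.

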1.4.6 Variables

Independent variable

1. Groups: Intervention group and standard care group
2. Time: At baseline, 1, 2 and 3 months of corrected age

Dependent variable

1. Motor performance
2. Neurodevelopment
3. Compliance

1.4.7 Data Collection

The study will be conducted after seeking ethical approval from Institutional Review Board (IRB), Khesar Gyalpo University of Medical Sciences of Bhutan (KGUMBS). The data will be collected at pediatric physiotherapy unit, JDWNRH. Preterm infants referred for high risk follow up clinic at Pediatric Physiotherapy Unit that evaluates neurodevelopmental outcome will be recruited. Oral and written information will be given to parents of the preterm babies fulfilling the inclusion criteria. Parents will be informed regarding the objectives, procedures, risk and benefits of the study. Informed consent will be taken from the parents prior to the study by the principal investigator. Strategies to achieve adequate participant enrolment to reach target sample size will be, establish a link between

the research team and mother and father of each of the subjects included, regardless of the group allocated since randomization.

Randomization will be performed by blindly drawing the slip from the container which will have equal numbers of same size and shape slips and will be performed by the research assistant who will not be responsible for any intervention nor outcome assessment. After randomization the infants in the control group will receive standard care and the infants in the intervention group will receive modified SPEEDI. The principal researcher will provide the modified SPEEDI. The research assistants shall be physical therapist or physical therapy assistants and occupational therapist who has over 2 years of experience in working with pediatric population and will be blinded to the group allocation since they will assess the outcome. These research assistants will be trained to use the measurement tools by the principal researcher. As the study participants are preterm infants, caution will be taken to avoid thermal stress to these infants by keeping the data collection room in pediatric physiotherapy unit warm. During the study process if there are amendments to the study protocol, the information shall be communicated with the IRB and the co-investigators of the study.

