Duration	20 mins/day	20 mins/day	20 mins/day
Frequency	5 days /week	5 days /week	5 days /week

Figure 4: Intervention Program

Activity	Stage 1	Stage 2
Activity1 – Looking at people and toys (4 minutes)	
 • Looking at people with support in supine • In side lying and swaddled 	
 • Tracking of caregiver in supine.
Activity 2- Tummy time (4 minutes)	
 • Tummy time on the caregiver’s chest 	
 • Tummy time on the floor
Activity 3- Holding head up (4 minutes)	
 • Head control with help from caregiver. • Head control by swaddling the baby. 	
 • Head control with less support from caregiver, unswaddled.
Activity 4- Kicking (4 minutes)	
 • Kicking with swaddle to support to support the arms. 	
 • Kicking with arms and legs free to move with slight support under the hips.
Activity 5- Toy play (4 minutes)	
 • With use of external support to bring hands and legs in middle. 	
 • Toy play without external support and variety of position such as supine and side lying.

Figure 5: Activity Description

The intervention will be provided as an outpatient based at JDWNRH by the principal researcher. It will require the parents to come to the hospital every month for the assessments and interventions. The parents will be called every week to ensure that they have no problem with the activities until the infant is 3 months of corrected age. The principal researcher will review and assess if the parents are performing the intervention correctly with the infant during the monthly visit. The parents in the intervention group will be advised not to share the activities and any information related to the intervention to other parents of preterm infants whom they might know.

They will be given appointment for assessment at different day or time and the information regarding the enrollment will be kept confidential.

Standard care group

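### If the person taking consent also delivers SPEEDI and slips are drawn down from 14 + 14, the recruiter can guess the next arm somewhat better than chance, and enrolment is not shielded from that knowledge

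*Combined protocol and SAP*

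**What the plan says.** Three roles matter, all set out in section 1.4.7.

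- Consent: "Informed consent will be taken from the parents prior to the study by the principal investigator".
- Treatment: "The principal researcher will provide the modified SPEEDI". Section 1.4.8.4 repeats it: "The intervention will be provided as an outpatient based at JDWNRH by the principal researcher".
- The draw: it "will be performed by the research assistant who will not be responsible for any intervention nor outcome assessment". The method is "blindly drawing the slip from the container which will have equal numbers of same size and shape slips".

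Section 1.4.5 sets the target: "a total of 28 infants born preterm would be required with 14 in each group".

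The visible text does not give the number of slips, say whether a drawn slip is returned, require eligibility to be signed and logged before the draw, or keep the running count from the recruiter. Nor does it say whether principal investigator and principal researcher are one person. Figure 3 (the study procedure) is not available in the text reviewed and may show the order of steps.

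On entry criteria, section 1.4.3 asks for medical stability at discharge without a definition, and section 1.4.4 excludes "Parent with physical and psychological problems", also without a threshold.

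**The concern.** The plan separates the slip draw from treatment and assessment, which is a real safeguard. It does not separate enrolment from treatment. Whoever treats every SPEEDI infant knows those allocations and can infer the control allocations by elimination. If that person also recruits, and the slips are a finite set drawn down, the past allocations show which arm has more slips left. Drawing blindly hides the individual slip but not the remaining proportions.

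Where a criterion needs judgement, the decision to enrol, or how firmly a family is encouraged, could then drift with the expected arm, perhaps without anyone noticing. Blinded assessment cannot correct this, because the groups would already differ at entry. The programme is carried out by parents at home, so parent motivation plausibly affects the outcome, and neither TIMP nor RNDA measures it.

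**Working it through.** **The plan's own figure.** Section 1.4.5 gives d = 1.29, 22 infants, and 28 after 20% dropout. A two-sample t-test with two-sided alpha 0.05 and 80% power (sidedness and power are assumed, since the text omits them and the G*Power figure is not shown) needs 11 per group, 22 in total, with power 0.821. Then 22 / (1 - 0.20) = 27.5, rounded up to 28, or 14 per group. The figure reproduces and this point does not change it.

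**Assumptions for the predictability check.** The container holds 14 + 14 slips; drawn slips are not returned; the recruiter knows every past allocation at each draw and names the arm with more slips left, choosing at random when the counts are equal.

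**Correct guesses.** The expected excess over 14 is 4^14 / (2 x C(28,14)) - 0.5. With 4^14 = 268,435,456 and C(28,14) = 40,116,600, this is 3.35 - 0.5 = 2.85. Expected correct guesses are 14 + 2.85 = 16.85 of 28, or 60.2%. Exact enumeration gives the same total and shows where the gain falls:

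| Draws | Average chance that the best guess is right |
|---|---|
| 1 | 50% |
| 1-14 | about 54% |
| 15-28 | about 66% |
| 26-27 | 74% |
| 28 | 100% |

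**Certain draws.** The expected number of draws left once one arm is exhausted is 2 x 14 / 15 = 1.87.

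**Uninformative draws.** The counts are tied, so nothing can be inferred, at 5.7 of the 28 draws on average.

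**Sensitivity to the slip count.** With 11 + 11 slips the results are similar: 13.47 of 22 correct (61.2%) and 1.83 certain.

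**Sensitivity to replacement.** If each slip were returned, every draw would be 50/50 and the argument would fail. Returned slips would, however, give exactly 14 and 14 with probability C(28,14) / 2^28 = 0.149, about 15%, which fits poorly with a plan for 14 in each group.

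**Possible false difference.** Suppose the enrolled infant's prognosis is shifted by +s SD when SPEEDI is expected, by -s SD when control is expected, and not at all at a tie. Correct minus incorrect guesses average 2 x 2.85 = 5.69. Dividing by 14 per group gives 5.69 / 14 = 0.41, so the expected false difference is 0.41 x s.

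- s = 0.25: 0.10 SD, and 0.10 / 1.29 = 8% of the planned effect.
- s = 0.5: 0.20 SD, and 0.20 / 1.29 = 16% of the planned effect.

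In simulation with 28 completers and no true effect, the two-sided error rate of a simple two-group t-test rises from 5% to about 6% at s = 0.25 and about 7% at s = 0.5. The value of s is an assumption; nothing in the documents informs it.

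**The case against.** Several points on the other side carry weight.

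*The premises are inferred.* A reader might infer that the protocol puts one person in both roles and specifies a fixed 14/14 container. It does neither. The two titles are never equated, the 14 per group is a sample-size target, and slip number and replacement are not given. Both readings are the natural ones, but the point is conditional on them.

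*Prediction is weak for most of the trial.* A reader might infer that the recruiter can foresee allocations throughout. The figures do not support that: guessing is near chance in the first half and certain only for about the last two infants.

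*Room for steering is limited.* Candidates are referred to the high-risk clinic, most exclusions are diagnoses or plain facts, agreeing to follow-up is the parents' decision, and the 40-week start limits how long a family could be deferred. Only a few criteria leave real discretion.

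*The design offers partial protection.* Blinded assessors measure TIMP at 40 weeks (section 1.4.8) and the analysis is a two-way mixed ANOVA (section 1.4.10). A stable difference in infant level would be visible at baseline and would cancel from the group-by-time interaction.

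All of this stands and lowers the size of the concern. It does not remove it. A shift that acts on trajectory, such as parent motivation, need not appear at baseline and would not cancel. Nor does anything in the visible text keep past allocations from the person taking consent.

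**Conclusion.** The concern holds conditionally, as a modest and avoidable risk of selection bias. It rests on two readings that the text supports but does not state: one person recruits and treats, and 14 + 14 slips are drawn without replacement. On those readings the recruiter gains about 10 percentage points over chance on average, mostly late in recruitment. The false difference of 0.41 x s also depends on an assumed s applied at every non-tied draw, including those where one arm is only one slip ahead. It bears mainly on factors that influence trajectory.

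A reader might go further and infer that enrolment will be steered or that the trial's result is biased. The documents give no evidence of either. What they show is that the separation protecting the draw does not extend to enrolment, and that this is cheap to put right.

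**What to change.** Amend section 1.4.7 as follows.

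1. One of the planned blinded research assistants, who does not know past allocations, confirms and signs the eligibility checklist and takes consent before the slip is drawn. No allocation exists at that moment, so this does not unblind the assistant.
2. The principal researcher takes no part in enrolment decisions until the slip has been drawn.
3. The randomising assistant alone holds the container and the tally.
4. Every screened infant is logged before the draw, with the reason for any non-entry.
5. The number of slips per arm is stated, and that drawn slips are not returned. If they are in fact to be returned, the section should say so, because the prediction argument would then no longer apply.

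The cost is brief consent training for an existing assistant and a notification to the IRB. No extra staff, infants or analyses are needed.
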